4. STUDY POPULATION

4.1. General Considerations

Approximately 160 subjects will be enrolled at 50-70 sites in up to five countries in the European Union, including United Kingdom, Germany and Poland. Subjects will be randomized only if they meet all of the inclusion criteria and none of the exclusion criteria.

4.2. Inclusion Criteria

Subjects enrolled in the study will have unilateral Meniere's disease as outlined by the American Academy of Otolaryngology - Head and Neck Surgery (AAO-HNS) Committee on Hearing and Equilibrium in 1995 (Committee on Hearing and Equilibrium, 1995).

To be eligible for this study, each of the following criteria must be satisfied with a "YES" answer (unless not applicable):

- 1. Subject is a male or female aged 18 to 85 years, inclusive.
- 2. Subject has a diagnosis of definite unilateral Meniere's disease by 1995 AAO-HNS criteria.
- 3. Subject self-reports active, definitive vertigo episodes for the 2 months prior to the study lead-in period.
- 4. Subject has documented asymmetric sensorineural hearing loss at screening or within the past 12 months according to AAO-HNS 1995 criteria defined as one of the following:
 - a. The arithmetic mean of hearing thresholds (pure tone average, PTA) at 250, 500 and 1000 Hz of 15 dB or more higher than the PTA of 1000, 2000, and 3000 Hz,
 - b. The arithmetic mean of PTA at 500, 1000, 2000 and 3000 Hz is 20 dB or more poorer in the ear in question than on the opposite side,
 - c. It is the judgment of the investigator that the subject's hearing loss meets reasonable audiometric criteria for hearing loss characteristic of Meniere's disease, and if so, it should be justified and documented.
- 5. Subject agrees to maintain their current treatments for Meniere's disease while on-study.
- 6. Female subjects of childbearing potential [i.e., not surgically sterile and/or not post-menopausal (≥12 months since last menstrual period and 45 years of age or older)] must have a negative urine pregnancy test before randomization. Women of childbearing potential who are not abstinent from sex with male partners may be entered into the study if they are using and willing to continue to use highly effective or "double barrier" contraceptive precautions for the duration of the study (e.g., oral contraceptives,

contraceptive implant or injection, intrauterine device, "double barrier" methods including male condom with diaphragm, male condom with cervical cap, male condom with spermicide, or diaphragm and spermicide).

- 7. Subject is willing to comply with the protocol and attend all study visits.
- 8. Subject is able to use the telephone to complete their daily diary.
- 9. Subject is able to provide written informed consent, including agreement to local privacy language requirements either within the informed consent or in ancillary documents compliant with local privacy laws before the initiation of any study-related procedures.

At the completion of the first 28 days of the lead-in period:

- 10. Subject has experienced and recorded at least 4 and a maximum of 22 definitive vertigo days during the 4-week lead-in period.
- 11. Subject completed at least 22 of 28 diary entries during the 4-week lead-in period.

4.3. Exclusion Criteria

To be eligible for this study, each of the following criteria must be satisfied with a "NO" answer: (unless not applicable):

- 1. Subject has an infection in the ear, sinuses, or upper respiratory system at the time of randomization.
- 2. Subject is pregnant or lactating.
- 3. Subject has a history of immunodeficiency disease.
- 4. Subject has active or recent (<1 month prior to screening) middle ear disease, including but not limited to: chronic otitis media, acute otitis media, middle ear effusions, middle ear atelectasis, or cholesteatoma.
- 5. Subject has an abnormality of the tympanic membrane in the affected ear that would increase the risk associated with intratympanic injection including but not limited to monomeric tympanic membrane.
- 6. Subject has a history of previous endolymphatic sac surgery.
- 7. Subject has a history of previous use of intratympanic gentamicin in the affected ear.
- 8. Subject has a history of tympanostomy tubes with evidence of perforation or lack of closure.
- 9. Subject has used systemic steroids within 1 month prior to entering the lead-in period.
- 10. Subject has had intratympanic steroids within 1 month prior to entering the lead-in period.
- 11. Subject has experienced an adverse reaction to intratympanic injection of steroids.
- 12. Subject has a hypersensitivity to dexamethasone or any of the excipients in OTO-104.
- 13. Subject has history of migrainous vertigo.

- 14. Subject has history of drop attacks.
- 15. Subject is not able to accurately identify and report episodes of vertigo.
- 16. Subject has any other clinically significant illness, medical condition, or medical history that, in the investigator's or the medical monitor's opinion, would prohibit the subject from participating in the study at screening or at the time of randomization.
- 17. Subject has used an investigational drug or device in the 3 months prior to screening.
- 18. Subject has a history of substance abuse within the preceding 6 months prior to screening.
- 19. Subject has previously been randomized to a trial of OTO-104.

5. RANDOMIZATION AND BLINDING

5.1. Overview

At the conclusion of the screening/lead-in period, eligible subjects will be randomly assigned to either OTO-104 or placebo in a 1:1 allocation ratio, stratified by gender, based on a computer-generated randomization schedule.

- 12 mg OTO-104; single, intratympanic injection
- Placebo; single, intratympanic injection

5.2. Enrollment Procedures

5.2.1. Assignment of Subject Identification Numbers

At the screening visit, Visit 1, subjects signing the informed consent will be assigned a unique subject identification number via the Electronic Data Capture system (EDC). Once assigned, the subject identification number will not be re-assigned and should not be changed. This number will be used to identify the subject throughout the study, including the screening and lead-in periods.

5.2.2. Treatment Assignment

Study sites will log in to the IWRS to execute each randomization after a subject has met all prerequisites for randomization and has completed all scheduled procedures for Day 1 (Visit 2). Study site personnel, who are blinded to treatment assignment, will receive a randomization notification indicating the kit number (packaged study drug), and the date and time of randomization for each subject. Once assigned, kit numbers cannot be re-assigned. Subjects will be considered enrolled into the study once they are randomized and assigned a unique randomization number.

Study sites will provide the information contained in the IWRS randomization notification to the unblinded qualified medical professional (QMP) responsible for preparation of the syringe containing study drug. The unique kit number provided by the IWRS will correspond to a kit of packaged study drug labeled with the identical kit number. The QMP will prepare the syringe

from the contents of the study drug package corresponding to the IWRS kit number according to the instructions in the study Pharmacy Binder. The subject identification number and kit number must both be recorded in the subject's record.

5.2.3. Randomization Algorithm

Subjects will randomized in a 1:1 ratio treatment groups stratifying by gender using a permuted block randomization algorithm. The randomization process will be deployed via an internet-based IWRS which is accessible 24 hours a day to authorized users. The subject's randomization number will determine the randomized treatment assignment. Numbered kits will be dispensed by the qualified medical professional based on the treatment assignment. Study drug kits will be labeled with a unique kit number using a separate and independent randomization algorithm.

5.3. Blinding

The study will be double-blinded. To maintain the blind for site personnel involved in study assessments, the following procedures will be followed:

Treatment syringes will be pre-loaded by an unblinded QMP. Each syringe will be prepared according to the detailed instructions in the Pharmacy Binder in a manner that prevents visualization of syringe contents by all other study staff through the use of a syringe overlabel. In addition, any interaction with subjects with regard to the collection, review or discussion of study assessments, with the exception of otoscopic exams, will be done by the study coordinator, audiologist or someone other than the QMP who prepared the syringe and the physician who administered the intratympanic injection of study drug. Every effort should be made to ensure that otoscopic exams are conducted by the physician who administered the study drug or another physician involved in the study, but not responsible for other assessments for the specific subject. Physicians administering study drug and conducting the otoscopic exams will be instructed not to discuss any potential visual differences observed in study material with subjects or study staff.

The blind should be broken only if knowing the subject's treatment allocation would facilitate specific emergency treatment. The physician who administered the study drug is unblinded at the time of injection. If the physician who administered the study drug is not available or does not recollect the treatment administered, the investigator can access the unblinded drug accountability records completed and retained by the QMP when preparing OTO-104 or placebo. In all cases, the investigator must contact the medical monitor as soon as is practical after unblinding has occurred and treatment initiated.

If the blind is broken, the subject will continue to be followed and evaluated per-protocol. The date, time, and reason for the unblinding must be documented on the appropriate page of the eCRF.

The randomization schedule or blocking factor(s) will not be revealed to study subjects, investigators, clinical staff, site managers or Sponsor representatives until all subjects have completed the trial and the database has been finalized by Otonomy.

6. DOSAGE AND ADMINISTRATION

6.1. Study Drug Administration

OTO-104 12 mg will be administered as a single, 0.2 mL intratympanic injection of 60 mg/mL OTO-104. The recommended injection procedure for intratympanic administration of OTO-104 in Meniere's disease subjects is as follows:

- 1. Place the subject in a recumbent position with the treated ear upwards. Anesthetize the tympanic membrane by covering the external surface of the posterior inferior quadrant with topical lidocaine/prilocaine cream until the tympanic membrane is numb. If applicable, suction away the topical lidocaine/prilocaine cream.
- 2. Using the 1 mL syringe pre-loaded with OTO-104 and equipped with a 25 or 26 gauge needle, insert the needle through the tympanic membrane with the bevel facing in an inferoposterior direction to a depth of approximately 2-3 mm just inferior to the round window niche, and with firm but gentle pressure, inject 0.2 mL taking care not to insert the needle further than necessary. Use of this technique will minimize the possibility of OTO-104 adhering to the underside of the tympanic membrane. Do not incise the tympanic membrane to form a ventilation hole as this is not needed due to the small injection volume.

6.2. Compliance

OTO-104 will be administered by site medical professionals as a single, intratympanic injection at Visit 2. Any deviations in administration will be documented in the source documents and the eCRF.

The site will maintain a log of all study drug dispensed and returned. Drug supplies for each subject will be inventoried and accounted for throughout the trial.

7. PRIOR, CONCOMITANT AND SUBSEQUENT THERAPY

Use of all concomitant medications will be recorded in the subject's eCRF. This will include all symptomatic relief medications for Meniere's disease symptoms, prescription drugs, herbal products, vitamins, minerals, and over-the-counter medications taken within 30 days before randomization, which will be considered prior therapy. Any concomitant medication deemed necessary for the welfare of the subject during the study may be given at the discretion of the Investigator except for those listed in Section 7.1. Any changes in concomitant medications will be recorded in the subject's eCRF.

7.1. Proscribed Therapy During the Study Period

The following therapies are prohibited during the study:

- Systemic corticosteroids
- Immunosuppressive medications
- Intratympanic injection other than that outlined in the current study

- Surgery for treatment of Meniere's disease
- Other investigational drug(s) or device(s)

Use of any of these proscribed therapies will be considered a protocol deviation.

7.2. Symptomatic Relief Medications

It is recognized that subjects may at times use certain medications for relief of symptoms related to Meniere's disease during the course of the study. Use of vestibular suppressants, anti-emetics and betahistine is allowed as symptomatic relief medications. The use of gentamicin or ear surgery at any time during the study will be considered a protocol deviation. Any changes reported by the subjects in concomitant medications should be recorded in the subject's eCRF.

8. STUDY EVALUATIONS

8.1. Study Procedures by Visit

8.1.1. Visit 1: Up to 14 days prior to initiation of lead-in period (Screening)

Because audiology, tympanometry and otoscopic exams are considered routine for this patient population, data obtained from assessments performed prior to documentation of informed consent can be used as screening data. In these cases, the data should have been collected within 14 days of initiation of the lead-in period.

The following assessments will be performed at Visit 1.

- Informed consent
- Confirm eligibility criteria
- Medical history
- Concomitant medications
- Vital signs
- Height and weight measurements
- Serum pregnancy test (for female subjects of childbearing potential only)
- Clinical laboratory test
- Tympanometry
- Audiometry
- Otoscopy
- C-SSRS assessment: Baseline version
- Review IVRS diary instructions with subject

8.1.2. Lead-In Period (Day -28 through -1 (+3 days))

The subject will record their daily vertigo experience during the entire lead-in period until randomization, ineligibility or withdrawal of consent. The determination of whether subjects meet Inclusion Criteria No. 10 and 11 will be conducted 28 days after initiation of the lead-in period.

8.1.3. Visit 2: Day 1 (Baseline/Dose Administration)

The following assessments will be performed at Visit 2.

- Confirm eligibility criteria
- Medical history
- Concomitant medications
- Vital signs
- Urine pregnancy test (for female subjects of childbearing potential only)
- Clinical laboratory test
- Tympanometry
- Audiometry
- Otoscopy
- TFI-25
- SF-36 Health Survey
- C-SSRS assessment, Since Last Visit version
- Randomize and administer OTO-104 or placebo (all assessments in the above list must be conducted prior to OTO-104 or placebo administration)
- Review subject IVRS diary instructions
- Adverse events (to be collected during or after OTO-104 administration)

8.1.4. Visit 3, 4: Week 4 and 8 (± 2 days) (Follow Up)

The following assessments will be performed at Visit 3 and 4.

- Concomitant medications
- Vital signs
- Tympanometry
- Audiometry
- Otoscopy
- TFI-25
- SF-36 Health Survey

- C-SSRS assessment, Since Last Visit version
- Review subject IVRS diary instructions
- Adverse events

8.1.5. Visit 5: Week 12 (± 4 days) (End of Study/Early Termination)

The following assessments will be performed at Visit 5.

- Concomitant medications
- Vital signs
- Urine pregnancy test (for female subjects of childbearing potential only)
- Clinical laboratory test
- Tympanometry
- Audiometry
- Otoscopy
- TFI-25
- SF-36 Health Survey
- C-SSRS assessment, Since Last Visit version
- Adverse events

8.2. Efficacy Evaluations

Efficacy assessments include:

- Characterization of Daily Vertigo Experience
- TFI-25 (exploratory endpoint)
- Short Form 36 Health Survey (SF-36) (exploratory endpoint)

To maintain the double-blind of the study, it is required that any interaction with subjects in the collection, review, or discussion of these assessments be done by the study coordinator or someone other than the investigator who administered the intratympanic injection of study drug. An exception may be made only if it involves the safety of the subject.

8.2.1. Daily Diary – Vertigo Experience

Subjects will record their daily vertigo experience via an IVRS daily diary by recording the severity of the worst vertigo episode experienced during the day, the effect of vertigo on their daily activities, and the number of vertigo episodes experienced during the day. Subjects eligible at screening will begin using the IVRS daily diary at the start of the lead-in period, and if randomized, will continue to record their daily vertigo experience throughout the remainder of the study. Subjects will be able to record missed diary entries for 1 day after a missed entry. Compliance with the IVRS vertigo diary will be monitored.

Using the daily vertigo scales developed by Gates (Gates, 2000; Gates, 2004; Gates 2005; Gates, 2006) and adapted to an IVRS, subjects are instructed to record the score that best corresponds to the worst vertigo episode experienced each day and the effect on their daily activities of their total vertigo experience that day using a 5-point scoring system:

Vertigo Severity Score

- 0 = Vertigo-free day
- 1 = Mild an attack lasting less than 20 minutes
- 2 = Moderate an attack lasting more than 20 minutes
- 3 = Severe an attack lasting more than 20 minutes and accompanied by nausea and/or vomiting
- 4 = The worst attack experienced to date

Effect of Vertigo on Activity Level

- 0 = Normal Activity
- 1 = Slight limitation
- 2 = Moderate limitation
- 3 = Sick at home
- 4 = Bed ridden

The occurrence of a definitive vertigo episode for a given day is defined as a recorded Vertigo Severity Score of 2 or more for that day. If multiple attacks occur on the same day, only the worst attack should be scored.

8.2.2. Tinnitus Functional Index (TFI-25)

The TFI-25 is a validated, 25-item questionnaire that can be used to quantify treatment-related change in tinnitus (Meikle et al., 2013; Henry et al., 2015). The total TFI score is a sum of the 25 items with a maximum score of 250, with higher scores representing greater perceived handicap. The 25 items can also be grouped into 8 subscales: 1) Intrusive, 2) Sense of Control, 3) Cognitive, 4) Sleep, 5) Auditory, 6) Relaxation, 7) Quality of Life, and 8) Emotional.

The TFI-25 will be administered to subjects at Visits 2, 3, 4, and 5.

8.2.3. Short Form 36 (SF-36) Health Survey

SF-36 is a validated, 36-item, multi-purpose, short-form health survey (Ware et al., 1993; Ware et al., 1994). It consists of 8 subscales: 1) Physical Functioning, 2) Role-Physical, 3) Bodily Pain, 4) General Health, 5) Vitality, 6) Social Functioning, 7) Role-Emotional, and 8) Mental Health.

The SF-36 health survey will be administered to subjects at Visits 2, 3, 4, and 5.

8.3. Safety Evaluations

Safety assessments include:

- Vital Signs, Height and Weight Measurements
- Clinical Laboratory Test
- Tympanometry
- Audiometry
- Otoscopy
- C-SSRS Assessment
- Concomitant Medications
- Adverse events (see Section 9)

8.3.1. Vital Sign, Height and Weight Measurements

Vital sign measurements (including systolic and diastolic blood pressure and pulse rate) will be collected at all study visits. Vital signs will be measured after subjects have been seated for 5 minutes and while subjects are in a sitting position. Height and weight will be measured at Visit 1 and weight will be measured again at Visit 5.

8.3.2. Clinical Laboratory Test

All clinical laboratory tests will be processed by a Central Laboratory.

Blood and urine samples for hematology, serum chemistry, urinalysis, and pregnancy tests will be prepared using standard procedures. Clinical laboratory testing will be completed at Visits 1, 2 and 5. In addition, female subjects of childbearing potential will have serum pregnancy test at Visit 1 and a urine pregnancy test at Visits 2 and 5.

The blood and urine samples will be used for the following tests:

Hematology: white blood cell count with differential, hemoglobin, hematocrit, platelet count, red blood cell count, mean corpuscular volume, mean corpuscular hemoglobin, and mean corpuscular hemoglobin concentration.

Serum Chemistry: albumin, alkaline phosphatase, alanine aminotransferase (ALT), aspartate aminotransferase (AST), blood urea nitrogen, carbon dioxide, calcium, chloride, creatinine, glucose, lactate dehydrogenase, phosphorus, potassium, sodium, total bilirubin, total protein.

Urinalysis: appearance, color, glucose, ketones, nitrite, pH, protein, specific gravity, occult blood, leukocyte esterase, and urobilinogen.

8.3.3. Tympanometry

Tympanometry assessments will be used to assess the mobility and compliance of the tympanic membrane, pressure and volume in the middle ear, and function of the tympanic membrane, ossicles and eustachian tube. Tympanograms will be completed in both ears at all study visits. Subjects wearing hearing aids should be instructed not to wear their hearing aids during the tympanometry assessment.

8.3.4. Audiometry

Audiometric assessments will be used to assess hearing function in both ears. Audiograms should be conducted at 500, 1000, 2000, 4000 and 8000 Hz for both air and bone conduction at all study visits. Both air and bone conduction thresholds will be assessed. Pure tone averaging bone and air conduction testing will be done at 500, 1000, and 2000 Hz frequencies. Subjects wearing hearing aids should be instructed not to wear their hearing aids during the audiogram.

Audiometric assessments must be conducted in accordance with American-Speech-Language-Hearing Association Guidelines (ASHA, 2005). Equipment calibration must be current and documented. The audiometric assessments must be conducted by a licensed audiologist or a qualified assistant with appropriate training under the direct supervision of a licensed audiologist.

8.3.5. Otoscopy

Otoscopic exams will be used to assess the auditory canal, the appearance of the tympanic membrane, and the healing of the intratympanic injection site. Otoscopic examinations will be performed in both ears at all study visits during the study by the physician. Presence and size of tympanic membrane perforations will be recorded. Perforations of the tympanic membrane will be captured as AEs only if the perforation increases in size and does not resolve by the end of the study. Subjects wearing hearing aids should be instructed not to wear their hearing aids during the otoscopic exam.

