9. ADVERSE EVENT REPORTING

Timely, accurate, and complete reporting and analysis of safety information from clinical trials will be conducted in accordance with Good Clinical Practice.

All AEs, including serious adverse events (SAEs) reported or observed during or after dosing with the study drug will be recorded on the AE page of the eCRF for all enrolled subjects. Information to be collected includes description of event, date of onset, investigator-specified assessment of the severity and relationship to study drug, date of resolution of the event, seriousness, any required treatment or evaluations, and outcome. Adverse events resulting from concurrent illnesses, reactions to concurrent medications, or progression of disease states must also be reported. Perforations of the tympanic membrane will be captured as AEs only if the perforation increases in size and does not resolve by the end of the study.

If the existing medical condition worsens at any time after application of study drug, it should be recorded as an AE.

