9.1. Adverse Event Classification Definitions

Adverse Event:

An AE is any unfavorable and unintended diagnosis, symptom, sign, syndrome or disease which occurs during the study, having been absent at baseline, or, if present at baseline, appears to worsen.

This includes any occurrence that is new in onset or aggravated in severity or frequency from the baseline condition, including abnormal results of diagnostic procedures and/or laboratory test abnormalities, which are considered AEs if they:

- result in discontinuation from the study
- require treatment or any other therapeutic intervention
- require further diagnostic evaluation (excluding a repetition of the same procedure to confirm the abnormality)
- are associated with clinical signs or symptoms judged by the investigator to have a significant clinical impact

Serious Adverse Event (SAE):

An SAE is defined as any untoward medical occurrence that:

- results in death,
- is life-threatening (Note: the term "life-threatening" refers to an event in which the subject was at risk of death at the time of the event rather than to an event which hypothetically might have caused death if it were more severe.),
- requires in-patient hospitalization or prolongation of existing hospitalization,
- results in persistent or significant disability/incapacity, or

• is a congenital anomaly/birth defect.

Medical and scientific judgment should be exercised in deciding whether expedited reporting is appropriate in other situations, such as important medical events that may not be immediately life-threatening or result in death or hospitalization but may jeopardize the subject or may require intervention to prevent one of the other outcomes listed in the above definition. These events should be considered serious.

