11.6.1. Adverse Events

The current version of Medical Dictionary for Regulatory Activities (MedDRA), as indicated in the Data Management Plan, will be used to code all AEs.

The primary analysis of AEs will consider only treatment-emergent AEs, events occurring for the first time, or worsening during or after the first dose of study drug. Subject incidence of TEAEs and SAEs will be tabulated by preferred terms and system organ class. Severity and relationship to study drug will also be presented. For summary tables, a subject who experiences the same coded event more than once is counted only one time for that coded event at the highest severity level. AEs will be presented by descending order of frequency in MedDRA system organ class and preferred term.

Subgroup analyses for age, race, and gender will also be examined provided a reasonable number of subjects in each subgroup are available for analysis. Listings of all SAEs, AEs leading to study withdrawal, and deaths on-study will also be included. Duration and outcome of each AE will be reported in subject listings.

Adverse events occurring during the lead-in period prior to exposure to study drug will be reported in data listings. Further details will be provided in the SAP.

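### The perforation rule keeps off the AE page an eardrum perforation that meets the protocol's own AE criteria (for example, it needed treatment) but closes before study end, and it names no reference size

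*Combined protocol and SAP*

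**What the plan says.** Section 8.3.5 (Otoscopy) has the presence and size of perforations recorded at every visit, in both ears. It then restricts AE capture: "Perforations of the tympanic membrane will be captured as AEs only if the perforation increases in size and does not resolve by the end" (meaning study end). Section 9 (Adverse Event Reporting) repeats the restriction: perforations are "captured as AEs only if the perforation increases in size and does not resolve by the end of the study".

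Section 9.1 defines an AE more broadly. It covers anything "new in onset or aggravated in severity or frequency from the baseline condition". It counts an abnormal examination result as an AE if the result leads to discontinuation, needs further diagnostic evaluation, comes with signs or symptoms the investigator judges clinically significant, or if such results "require treatment or any other therapeutic intervention". None of these depends on whether the event later resolves.

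Two other sentences bear on the point. Section 9 adds: "If the existing medical condition worsens at any time after application of study drug, it should be recorded as an AE". Section 11.6.1 limits the main AE analysis to "events occurring for the first time, or worsening during or after the first dose of study drug".

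The injection itself makes a hole. Section 6.1 describes a syringe "equipped with a 25 or 26 gauge needle, insert the needle through the tympanic membrane". At Visit 2, otoscopy is on a list for which "all assessments in the above list must be conducted prior to OTO-104 or placebo administration" (Section 8.1.3). The next scheduled otoscopy is at Week 4 (Section 8.1.4).

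**The concern.** The restriction joins two conditions, enlargement and non-resolution, and introduces them with exclusive wording. A perforation that fails either one is not an AE, whatever else happened to the subject. A perforation that had to be treated and then healed is the kind of local harm a reader expects to find in the AE tables of an intratympanic product, yet this rule removes it because it healed.

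The loss would be specific. The event would get no severity grade (Section 9.1.1) and no causality assessment (Section 9.1.2). It would not appear in the treatment-emergent AE tables (Section 11.6.1). If perforations code to the ear and labyrinth system organ class, which is an assumption, it would also be absent from the regular blinded review of AEs in that class (Section 14.7). Describing safety is the trial's only secondary objective (Section 2.2).

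The rule is also hard to apply consistently, because nothing says which earlier size an increase is judged against.

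**Working it through.** No statistical calculation applies, and the plan has no figure of its own to reproduce. The check sets the rule beside the AE definition, case by case, for a perforation in the injected ear that was absent before injection.

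| Course of the perforation | AE under 8.3.5 and 9? | AE under 9.1? | Conflict |
|---|---|---|---|
| Enlarges, meets a 9.1 criterion, closes | No | Yes | Firm |
| Does not enlarge, meets a 9.1 criterion, closes | No | Yes | Firm |
| Enlarges, meets no listed criterion, closes | No | Depends on reading | Uncertain |
| Does not enlarge, meets no listed criterion, open at Week 12 | No | Depends on reading | Uncertain |
| Does not enlarge, meets no listed criterion, closes | No | Expected puncture | None intended |
| Enlarges, open at Week 12 | Yes | Not excluded | None |

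The uncertain rows turn on how Section 9.1 is read. If a perforation is an occurrence in its own right, being new or aggravated is enough. If it is an abnormal examination result, one of the four listed consequences is needed. The first two rows are firm because a perforation that required treatment is an AE on either reading.

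**Reference size.** There are three candidates, and the documents choose none.

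- The needle puncture is the natural reading, but no scheduled examination measures it: Day 1 otoscopy precedes the injection.
- The first post-injection examination is at Week 4, Day 28 ± 2, so Day 26 to 30. That is 26 − 1 = 25 to 30 − 1 = 29 days after injection. Enlargement before then would be missed unless an unscheduled visit caught it.
- Against the pre-injection examination, any hole still visible in a previously intact membrane is an increase.

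**Timing.** A perforation that closes is settled as a non-AE at closure. One that has enlarged and is still open cannot be classified until the last visit. Table 1 sets that visit at Day 84 (+4), so Day 84 to 88. Section 8.1.5 gives ±4 days, so Day 80 to 88. These two windows themselves disagree.

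- Enlarged and open at Week 4 (Day 26 to 30): 84 − 30 = 54 to 88 − 26 = 62 days under Table 1; 80 − 30 = 50 to 62 days under Section 8.1.5.
- Enlarged and open at Week 8 (Day 54 to 58): 84 − 58 = 26 to 88 − 54 = 34 days under Table 1; 80 − 58 = 22 to 34 days under Section 8.1.5.

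**Number affected.** The injection punctures the membrane in both arms (planned 160 subjects, 80 per arm), but the documents give no rate of perforation, enlargement or closure. No count follows.

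**The case against.** The strongest reply is that this is a deliberate carve-out. The same rule appears in two sections, one of them the AE reporting section, and its wording is that of an exception. A needle puncture is the expected result of dosing in both arms, and recording each one as an AE would add noise. That stands as a reason to exempt an uncomplicated puncture. It does not explain exempting one that needed treatment, and Section 9.1 is not marked as giving way.

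Four stronger readings are tempting, and the documents do not support them.

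- A reader might infer that every perforation that enlarges and then closes is wrongly dropped. If it is read as an examination finding, Section 9.1 would not make it an AE without treatment, work-up, discontinuation or significant symptoms.
- A reader might take Section 11.6.1 as a second contradiction. It selects among AEs already captured; it does not say what to capture.
- A reader might see the sharpest conflict in the worsening sentence of Section 9. The existing condition there may mean only disease present before dosing, which a puncture made by the injection fits poorly.
- A reader might infer that perforation data are lost or that oversight fails. Presence and size are recorded. Section 11.6.3 tabulates otoscopic classifications by arm and visit, and changes to the endpoint visit where relevant. Drug treatment appears among concomitant medications (Section 7). The blinded safety review in Section 14.7 is not confined to AEs.

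These points narrow the concern but do not remove it. Section 11.6.3 names neither perforation nor size, and does not separate treated from untreated ears as Section 11.6.4 does for audiometry. Section 11.6.1 leaves further detail to the SAP, but a table there cannot restore severity and causality grades that sites were told not to record. The rule is common to both arms. However, Section 5.3 allows otoscopy by the injecting physician, who is unblinded, so a size judgement without a stated reference is best avoided.

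**Conclusion.** The point holds in a limited form. As written, Sections 8.3.5 and 9 exclude from AE recording a post-injection perforation that meets a Section 9.1 criterion and closes before Week 12. AE-based outputs are then incomplete for a local effect of the injection. Two further cases are less certain conflicts: enlargement that closes with no listed consequence, and a perforation that has not enlarged but is still open at Week 12. The missing reference size is a separate and definite gap.

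The size of the understatement is unknown. The conclusion assumes that sites follow the restriction literally; where a site applies Section 9.1 instead, recording will differ between sites. Nothing here shows bias between arms, and efficacy is unaffected. The point is worth correcting because the correction is cheap, not because a large distortion has been shown.

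**What to change.** 1. Reconcile Sections 8.3.5 and 9 with Section 9.1. A perforation that is new or worsened since the pre-injection examination and meets a Section 9.1 criterion should not be excluded merely because it resolves by study end.
2. Keep the intended exemption, and say in Section 9.1 that it is one: an uncomplicated injection puncture that closes is not an AE.
3. State in both sections what an increase in size is measured against, using examinations that are scheduled or recorded, including unscheduled visits. The puncture cannot serve as a measured reference under the present schedule.
4. Limit the rule to findings new or worsened since baseline, so that an unchanged baseline perforation in either ear is not captured. Section 9.1 would not count it.
5. Add one table of perforation presence and size by arm, visit and treated or untreated ear, from the otoscopy data already collected.

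The cost is a reworded sentence in two sections, an exception line, a line in the eCRF guidelines, one table, and a protocol amendment with ethics committee approval (Section 14.1). Some additional AEs will be reported in both arms; their number cannot be estimated from the documents. No new visit or examination is needed.
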